4.2.8.6 Subgroup Analysis

[figure not shown]
Subgroup analyses will be performed for the 16 weeks analysis timepoint. See Section 4.2.1.7 for details. The following variables listed for primary endpoints will not be included: Alcohol consumption, Nicotine consumption, S-Cystatin-C and Ceruloplasmin

CCI

CCI

CCI

4.2.16 Exploratory Endpoint – Time to cardiovascular event

4.2.16.1 Definition

Estimands

The following attributes define the estimand used to evaluate the primary analysis of this endpoint.

- **Endpoint:** Time to the first occurrence of any event in the composite event variable consisting of HF hospitalisation, urgent HF visits with requirement for additional loop diuretic treatment, MI, cardiovascular deaths, and all-cause mortality.
- **Treatment:** Randomised treatment group (regardless of actual received treatment), AZD4831 2.5mg/5mg or placebo.
- **Population:** Subjects aged ≥ 40 years with an established diagnosis of HF with LVEF $> 40\%$, and at least one or more of structural heart disease, signs of increased left ventricular filling pressure, signs of significant diastolic dysfunction, or a recent hospitalisation for decompensated HF. Implemented by FAS.
- **Population-level summary:** Kaplan-Meier (KM) estimate by treatment group, difference in KM estimate between treatment groups and hazard ratio (HR) between treatment groups.
- **Handling of intercurrent events:** Treatment policy strategy combined with composite variable strategy.
 - Initiation or change of concomitant medication and permanent premature discontinuations will be handled by a treatment policy strategy, i.e., ignoring these intercurrent events, implemented by including all available data.

4.2.16.2 Derivations

Time (in days) from randomisation to first event in composite variable will be derived. In addition, time (in days) from randomisation to first event for each individual component is derived.

The Planned treatment period will be used. See Section 3.3.1.8 for censoring rule.

Deaths reported as ‘cause undetermined’ will be included as non-CV deaths in the analysis.

4.2.16.3 Handling of Dropouts and Missing Data

Any missing data will not be imputed. See Section 3.3.1.8 for details on time-at-risk and censoring.

4.2.16.4 Primary Analysis of Exploratory Endpoint

The risk for an event at 48 weeks will be evaluated under the estimand defined in Section 4.2.16.1 and estimated using KM % estimates. AZD4831 Total and placebo will be compared using a Cox regression model with factors for treatment group and stratified by neutrophil count. The Efron method for ties and p-value based on the score statistic will be used.

The composite event and individual components will be analysed separately using the same model and the contribution of each component of the primary composite endpoint to the overall treatment effect will be presented. For the individual component analyses, all first events of the given type will be included irrespective of any preceding non-fatal composite event of a different type.

For the interim analysis/es, the risk for an event at 16 weeks will be estimated.

Presentation

The number of events, Kaplan-Meier %, HR with 95% CI and p-value will be presented. KM% estimates of the cumulative distribution function of subjects with the composite event as well as the individual component will be plotted comparing all treatment groups.

[figure not shown]
A series of horizontal black bars of varying lengths, likely representing redacted text or code. The bars are arranged vertically, with some shorter bars at the top and longer bars towards the bottom. The first bar on the left has a small red 'cc' label in the top-left corner.

CCI

CCI	[REDACTED]	[REDACTED]	[REDACTED]	[REDACTED]	[REDACTED]	[REDACTED]
	[REDACTED]	[REDACTED]	[REDACTED]	[REDACTED]	[REDACTED]	[REDACTED]
	[REDACTED]	[REDACTED]	[REDACTED]	[REDACTED]	[REDACTED]	[REDACTED]
	[REDACTED]	[REDACTED]	[REDACTED]	[REDACTED]	[REDACTED]	[REDACTED]
	[REDACTED]	[REDACTED]	[REDACTED]	[REDACTED]	[REDACTED]	[REDACTED]

A horizontal bar chart consisting of 20 solid black horizontal bars of varying lengths. The bars are arranged in a single row, with some shorter bars on the left and right sides and longer bars in the center. The lengths of the bars decrease from left to right and then increase again towards the right end of the chart.

CCI

CCI [REDACTED]
[REDACTED]
[REDACTED]
[REDACTED]
[REDACTED]
[REDACTED]
[REDACTED]
[REDACTED]

4.3 Pharmacodynamic Endpoint(s)

Inflammatory biomarkers will be analysed as described in Sections 4.2.8 and 4.2.14.

4.4 Pharmacokinetics

Plasma concentrations of AZD4831 will be presented as described in Section 4.2.7.

4.5 Immunogenicity

Not applicable.

4.6 Safety Analyses

The domain safety covers exposure, adverse events, clinical laboratory, vital signs, and electrocardiogram (ECG).

Tables, figures, and listings are provided for SAS unless otherwise stated. All tabulations of safety data (AEs, laboratory parameters, vital signs, and ECG) will be based on both the On-treatment period and On-study period respectively unless otherwise stated.

The analyses will be presented for AZD4831 2.5mg, AZD4831 5mg, AZD4831 Total (pooled treatment groups AZD4831 2.5mg and 5mg) and placebo, unless otherwise stated.

Safety estimand definition

The aim with the analyses of safety data is to assess the general safety objective; this will be done for a hypothetical scenario where study treatment is not prematurely discontinued. Two different handling of intercurrent event strategies are considered complementary to assess this hypothetical scenario for all safety endpoints:

- On-treatment; unbiased under the assumption that censoring following premature treatment discontinuation is non-informative. Note that this approach could also be described as handling premature treatment discontinuation with a hypothetical strategy.
- On-study; unbiased under the assumption that the risk for an event is independent of continued treatment. Note that this approach could also be described as handling premature treatment discontinuation with a treatment policy strategy.

Hence, the general safety objective will be assessed through two complementary estimands with respect to handling of the intercurrent event of premature discontinuation of study treatment, defined by the following attributes:

- **Population:** Subjects with an established diagnosis of HF with LVEF > 40%, as defined by the inclusion and exclusion criteria, who have received at least one dose of IP. Implemented using the safety analysis set.
- **Treatment:** Actual treatment group (i.e., not necessarily the treatment a subject was randomised to), AZD4831 2.5mg/5mg or placebo.
- **Intercurrent events:**
 - Premature study treatment discontinuation: All analyses will be provided using two complementary strategies:
 - Hypothetical strategy: Premature study treatment discontinuation cannot occur, implemented by censoring data after premature study treatment discontinuation + 14 days, using the On-treatment analysis period (Section 3.3.1.5).
 - Treatment policy strategy: Ignoring study treatment discontinuation, implemented by including all available data, using the On-study analysis period (Section 3.3.1.5).
 - Initiation or change of concomitant medication, including rescue medication: Will be ignored, i.e., handled using a treatment policy strategy.
 - Death: Except for assessment of mortality, will be handled by a hypothetical strategy as it cannot occur, implemented by censoring time to event data at time of death and not imputing any data after death.
- **Population level summaries:** Distribution of endpoints by treatment group for all safety variables. Kaplan-Meier (KM) estimate for event by treatment group, difference in KM estimate between treatment groups and hazard ratio (HR) between treatment groups for AEs.

Table 4. Overview of safety objectives, endpoints and estimands for Part A

Statistical category	Endpoint	Population	Handling of inter-current events	Population level summary (analysis)	Details in section
Objective 1: To assess the safety and tolerability of AZD4831 as compared with placebo in patients with HF					
Safety	Safety and tolerability will be evaluated in terms of AEs, Vital signs, Clinical laboratory, and ECG.	SAS	Hypothetical strategy; Treatment policy strategy	Distribution of endpoints by treatment group for all safety variables. KM estimate for event	4.6

Statistical category	Endpoint	Population	Handling of inter-current events	Population level summary (analysis)	Details in section
	
Assessments related to AEs will cover:
 
 • Occurrence/Frequency • Seriousness • Death • AEs leading to discontinuation of IMP • AEoSIs related to skin reactions, including maculopapular rash, and infection 
Vital signs parameters include blood pressure, pulse rate, and body temperature; assessments will cover:
 
 • Observed value • Absolute change from baseline values over time • Orthostatic blood pressure 
A complete list of laboratory parameters is presented in Section 8.2.4 of the CSP; assessments will cover:
 
 • Observed value • Absolute change from baseline values over time • Treatment-emergent changes in selected laboratory parameters 
Electrocardiogram measurements assessments will cover:
 
 • Investigator evaluation 			by treatment group, difference in KM estimate between treatment groups and HR between treatment groups for AEs.	

4.6.1 Exposure

4.6.1.1 Definitions and Derivations

Duration of exposure (days) to study drug will be calculated for each subject as

$$\text{Duration of exposure (days)} = \text{date of last dose} - \text{date of first dose} + 1.$$

Dose interruptions will not be taken into consideration for calculation of duration of exposure.

Total time of exposure (subjects-years) is calculated as

$$\text{Total time of exposure} = \text{sum}(\text{duration of exposure for each subject}) \div 365.25$$

4.6.1.2 Presentation

Duration of exposure and Total time of exposure will be presented descriptively by treatment group and in total.

Total exposure will be presented categorically by cumulative categories by every 28th day from Day 1 to Day 337. These categories are cumulative, and subjects will be included in all categories that apply to them.

A figure of exposure over time will be presented, with one line for each treatment group, and percentage of subjects still exposed on the y-axis and time from first dose on the x-axis. At a given time t, the curve will show the percentage of subjects with exposure time >t.

In addition, KM% estimates of the cumulative distribution function of subjects who have discontinued IP will be plotted comparing all treatment groups, applied on the planned treatment period.

Listings

Subjects who receive IP which is not consistent with the treatment he or she was randomised to receive will be listed.

4.6.2 Adverse Events

4.6.2.1 Definitions and Derivations

Adverse event will be assigned to the analysis period based on the onset date, as defined in Section 3.3.1.5.

Adverse events will be classified by SOC and PT and coded using Medical Dictionary for Regulatory Activities (MedDRA).

Risk for an event will be estimated using KM% estimates. Comparisons of risk for an event between the treatment groups will be estimated by HRs with 95% CIs based on a Cox regression model with a factor for treatment group, and difference in KM%. A subjects first event that occurs during the On-treatment or On-study period, respectively, will be included in the analysis. All subjects who are event free for the given AE (or AE category) will be censored according to the definitions in Sections 3.3.1.5 and 3.3.1.8.

Any AE

Defined as an AE reported with an onset date within the defined period.

Any SAE

Defined as an AE reported as serious, irrespective of outcome.

SAEs with outcome death

Defined as an AE with reported outcome as 'Fatal', there may be more than one AE with outcome death for a subject. The onset date of the AE determines the analysis period, irrespective of date of death.

AEs leading to discontinuation of IP

Defined as an AE with action taken IP reported as drug permanently discontinued. The onset date of the AE determines the analysis period, irrespective of date of discontinuation of IP.

AEs possibly related to IP

Defined as an AE that is reported as "reasonable possibility AE caused by IP". If this evaluation is missing, it will be counted as an AE possibly related to IP.

AEs by maximum intensity

AEs will be classified by the reported maximum intensity, "Mild", "Moderate" and "Severe". If this maximum intensity evaluation is missing, it will be counted as "Severe".

Adverse events of special interest

The following two groups of adverse events are Adverse events of special interest (AEoSI):

- Infections: will be identified by the SOC "Infections and infestations".
 - The pathogen specific High level group term (HLGT) "Fungal infectious disorders".
- Skin reactions, including maculopapular rash:
 - Skin reactions/rashes considered maculopapular (described as macules/papules under the morphology/appearance question).
 - Skin reactions/rashes not considered maculopapular (not described as macules/papules under the morphology/appearance question).

4.6.2.2 Presentation

For all AE tables, unless otherwise stated, the number and percentage of subjects experiencing an event along with Kaplan-Meier percentages at 16 and 48 weeks will be presented for all treatment groups. In addition, KM% differences and HR together with 95% confidence intervals will be presented for the comparisons of each active treatment group to placebo. Percentages will be calculated with number of subjects in SAS as denominator, and subjects will only be counted once per category, regardless of the number of AEs satisfying each condition.

Tables where AEs are presented by SOC and PT will be sorted by international order for SOC and alphabetical order for PT.

In addition, KM% estimates of the cumulative distribution function of subjects with AEoSIs will be plotted comparing all treatment groups. Overall summary of AEs

The following categories will be presented in the overall summary:

- any AE,
- any SAE,
- any SAE with outcome death,
- any AE leading to discontinuation of IP, and
- any AE possibly related to IP (as assessed by investigator).

Any AE leading to discontinuation of IP category will only be analysed for the On-treatment period.

By SOC and PT

Separate AE tables by SOC and PT will be presented for the following categories:

- any AE,
- AEs possibly related to IP,
- AEs leading to discontinuation of IP,
- AEs by cumulative maximum intensity (any, moderate or severe, severe),
- any SAE,
- SAE with outcome death, and

- AEs of special interest.

Most common AEs

A table of the number and percentage, and KM% at 16 and 48 weeks of the most common adverse events by PT (frequency of > 5%). This table will be sorted by decreasing frequency in AZD4831 5mg arm.

Most common non-serious AEs

A table of non-serious AEs occurring in more than 5% of subjects in any treatment group will be presented, by SOC and PT.

AEs of special interest

A mapping of the AEoSIs to Preferred terms will be presented.

For each of the SOC Infections and infestations and the HLGT Fungal infectious disorders, an overall summary, and any AE and SAE by PT will be presented. In the overall summaries, AEs by cumulative maximum intensity (any, moderate or severe, severe) will be presented in addition to categories described under Overall summary of AEs.

Skin reactions will be presented by a summary of the following categories of skin reactions:

- any skin reaction/rash
- any maculopapular skin reaction/rash leading to permanent premature IP discontinuation by cumulative maximum CTCAE grade (any, 2 or 3, 3), and
- any non-maculopapular skin reaction/rash leading to permanent premature IP discontinuation (SAEs and generalised skin reaction/rash)

For maculopapular skin reaction/rash an overall summary, maculopapular AEs by PT and maculopapular SAEs by PT will be presented. In the overall summary, AEs by cumulative maximum intensity (any, moderate or severe, severe) and AEs by cumulative maximum CTCAE grade (any, 2 or 3, 3) will be presented in addition to categories described under Overall summary of AEs.

In addition, maculopapular AEs and SAEs will be presented by cumulative maximum CTCAE grade (any, 2 or 3, 31, 2, 3), on PT level.

For other skin reactions/rashes (excluding maculopapular skin reactions/rashes) an overall summary, AEs by PT and SAEs by PT will be presented. In the overall summaries, AEs by

cumulative maximum intensity (any, moderate or severe, severe) will be presented in addition to categories described under Overall summary of AEs.

Key subject information

Key subject information will be presented for subjects with

- SAEs with outcome death,
- any SAEs, and
- AEs leading to discontinuation of IP for the full study period.

Listings

Adverse events listings will be presented for

- each individual AE,
- subjects with AEoSIs related to skin reactions (including maculopapular rash), and
- AEs reported for subjects who received the incorrect IP, i.e., not the randomised IP.

Narratives

Narratives will be generated for all deaths, AEs leading to discontinuation of IP, AEs of special interest and SAEs.

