3.2 Part B

The following information in Table 5 relates to the objectives of Part B of the study.

Table 5 Objectives and Endpoints – Part B

Objectives	Endpoints/Variables
Primary	
To assess the effect of AZD4831 on heart failure symptoms	KCCQ-TSS, primary assessment at 24 weeks
To assess the effect of AZD4831 on functional capacity	6MWD, primary assessment at 24 weeks
Secondary	
To assess the effect of AZD4831 on diagnostic biomarkers	NT-proBNP, primary assessment at 24 weeks
To assess the effect of AZD4831 on inflammatory biomarkers	hsCRP and IL-6, primary assessment at 24 weeks

Table 5 Objectives and Endpoints – Part B

Objectives	Endpoints/Variables
Safety	
To assess the safety and tolerability of AZD4831	
 • Occurrence and time to first occurrence of AE, SAE, SAE with outcome death, AE leading to discontinuation of study intervention, possibly related AE as assessed by investigator, possibly related SAE as assessed by investigator. • Observed laboratory value, change from baseline and time to first treatment emergent abnormality. • Observed vital sign value, change from baseline, and time to first treatment emergent abnormality. • Observed ECG abnormalities, change from baseline, and time to first treatment emergent abnormality. • Occurrence and time to first occurrence of AEoSI categories: skin reactions, including maculopapular rash, and infection.
Tertiary	
CCI 	                          [figure not shown] 40%. The study will consist of 2 separate parts; see the study flow charts in Figure 1 and Figure 2.

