- Death: With the exception of assessment of mortality, will be handled hypothetically as it cannot occur, implemented by censoring time to event data at death and not imputing any data after death.

Population level summaries: Distribution of endpoints by treatment group, Kaplan-Meier estimate for endpoints by treatment group, difference in Kaplan-Meier estimates between treatment groups and treatment hazard ratios.

This estimand requires that to the extent possible, randomised subjects are followed up regardless of study intervention compliance and adherence to the study protocol.

Adverse Events

All AEs will be classified by system organ class, high level group term, high level term, and preferred term according to MedDRA.

AEs will be presented for each treatment group by SOC and/or PT, covering number and percentage of subjects reporting at least one event. An overview of AEs will present for each treatment group the number and percentage of subjects with any AE, AEs with outcome of death, serious AEs, and AEs leading to discontinuation of IP. Separate AE tables will be provided taking into consideration seriousness, death, and events leading to discontinuation of IP. An additional table will present number and percentage of subjects with most common AEs. Most common (eg, frequency of $>x\%$, $\geq x\%$) will be defined in the SAP. In accordance with the requirements of the FDA, a separate table will present non-serious AEs occurring in more than 5% of subjects in any treatment group. Key subject information will be presented for subjects with AEs with outcome of death, serious AEs, and AEs leading to discontinuation of IP. An AE listing for the safety analysis set will cover details for each individual AE. AEoSIs related to skin reactions, including maculopapular rash, and infection will be presented. Full details of AE analyses will be provided in the SAP.

All safety analyses are descriptive; hence no p-values will be presented for any safety analyses, and confidence intervals are provided as an illustration of precision of the estimate. Hazard ratio between treatment groups will be based on a Cox proportional hazards regression model with a factor for treatment group.

Treatment emergent

For Part A, the definition for treatment emergent events will be provided in the SAP.

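### Kaplan-Meier percentages for AEs leading to discontinuation of IP censor competing events, so they modestly overstate the cumulative incidence, and the stated strategy does not fit this endpoint

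*SAP*

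**What the plan says.** SAP 4.6.2.1 defines the event by what was done with the drug: "Defined as an AE with action taken IP reported as drug permanently discontinued". It sets one estimator for AEs generally: "Risk for an event will be estimated using KM% estimates". In the overall summary, SAP 4.6.2.2 then restricts this category: "Any AE leading to discontinuation of IP category will only be analysed for the On-treatment period".

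Under SAP 3.3.1.5 the On-treatment period ends at the earliest of 14 days after last dose, consent withdrawal or death. Under 3.3.1.8 event-free participants are censored there. SAP 4.6 gives the strategy behind the period: "Premature study treatment discontinuation cannot occur, implemented by censoring data after premature study treatment discontinuation + 14 days". Deaths are also censored. Protocol 9.4.3 says so ("implemented by censoring time to event data at death and not imputing any data after death"), and SAP 4.6 has the same rule.

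AE tables do not show KM alone. SAP 4.6.2.2 states that "the number and percentage of subjects experiencing an event along with Kaplan-Meier percentages at 16 and 48 weeks will be presented", with KM% differences and hazard ratios against placebo, each with a 95% CI. For the crude figures, "Percentages will be calculated with number of subjects in SAS as denominator". The disposition table in SAP 4.1.1.2 separately counts treatment stops by reason.

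**The concern.** For most AE types, a participant who stops drug can still have the event, so censoring shortly after the stop has a clear, if hypothetical, meaning. This category is different. Someone who stopped by own decision or for non-compliance, or who died on drug, can never again have an AE whose consequence is stopping the drug. KM treats these participants as still able to have one. It therefore estimates the share who would stop for an AE if nobody stopped for any other reason and nobody died.

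The strategy is also contradictory for this endpoint. In a world where premature discontinuation cannot occur, the risk of an AE leading to it is zero. With the On-study analysis dropped for this row of the overall summary, no other strategy remains there.

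The share stopping because of an AE is a main tolerability figure. Maculopapular rash of grade 1, 2 or 3 requires permanent discontinuation (protocol 7.1), and safety is part of the Part B dose decision (protocol 4.3). The KM% difference is the only absolute contrast with placebo for which a CI is planned.

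**Working it through.** The documents give no discontinuation rate or KM figure for this category, so there is no stated value to reproduce. The size has to be shown under assumptions.

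**Inputs**
- From protocol 9.2: 660 randomised and about 600 with complete safety data, so 60/660 = 9.1% attrition. This is the only documented anchor. It is used once, for all competing events together (stops for other reasons plus deaths), and is not itself a drug-stopping rate.
- From protocol 9.2: 1:1:1 allocation, so about 220 per arm and 440 in the pooled AZD4831 group.
- Assumed: AE-stop risk of 8-15% on the KM scale at week 48, with constant hazards.

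**Formulas** (time in units of the 48-week period)
- AE-stop hazard h = -ln(1 - KM); competing hazard c = -ln(1 - 0.0909) = 0.0953.
- Actual cumulative incidence = h/(h + c) × [1 - exp(-(h + c))].
- SE of the percentage, taken as binomial = √[KM(1 - KM)/n].

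**Worked case, KM = 12%**
- h = -ln(0.88) = 0.1278; h + c = 0.2231; exp(-0.2231) = 0.88 × 0.9091 = 0.800.
- Incidence = 0.1278/0.2231 × 0.200 = 11.46%.
- Gap = 12.00 - 11.46 = 0.54 points.
- SE at n=440 = √(0.12 × 0.88/440) = 1.55 points, so the gap is 0.54/1.55 = 0.35 SE.

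| KM at week 48 | Incidence | Gap (points) | Gap in SE, n=440 | Gap in SE, n=220 |
|---|---|---|---|---|
| 8% | 7.64% | 0.36 | 0.28 | 0.20 |
| 12% | 11.46% | 0.54 | 0.35 | 0.25 |
| 15% | 14.33% | 0.67 | 0.40 | 0.28 |

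**Week 16.** With one third of each hazard, KM = 1 - exp(-0.0426) = 4.17% and incidence = 4.11%, a gap of 0.07 points.

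**14-day lag.** A simulation that censored most non-AE stops at last dose plus 14 days gave almost the same KM as immediate censoring (10.51% against 10.50%, where 10.0% actually stopped for an AE and 9.1% had a competing event).

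**Early AE stops.** With all AE stops in the first 4 weeks and competing events spread over 48 weeks, the simulated gap was 0.02 points or less.

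**Wider range.** The largest simulated gap was 1.8 points (16.8% against 15.0%), which needs an assumed 20% with competing events. The documents give no support for that rate.

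**Between-arm contrast.**
- With 9.1% competing events in both groups and assumed KM of 12% (n=440) and 6% (n=220), the gaps are 0.54 and 0.27 points. The KM% difference is then off by 0.27 points. Its SE is √(0.12 × 0.88/440 + 0.06 × 0.94/220) = 2.23 points, so the error is 0.12 SE.
- If both groups have KM 12% but competing events are 5% and 15%, KM shows no difference while the actual incidences are 11.7% and 11.1%.

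**The case against.** The strongest reply is that the right number is already in the table. A reader might infer that this category is analysed by KM alone and that whatever percentage is reported is too high. The documents do not support that. The crude n (%) on the full Safety analysis set stands beside the KM%, and disposition counts stops by reason. Every Part A participant has the same planned 48 weeks, so at the final analysis the crude percentage is the share who stopped for an AE. This stands, and it limits the point to the KM% and the KM% difference.

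It does not dispose of the point. The crude percentage has no planned difference or CI. It also does not equal a fixed-time incidence at an interim with incomplete follow-up, and interims may begin once 150 randomised participants could have reached week 16 (SAP 3.1 and 5).

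Other stronger readings also fail:
- No KM plot of this category is planned. The plots are for AEs of special interest (4.6.2.2) and for all IP discontinuation (4.6.1.2).
- The On-treatment restriction appears under the overall summary and is not repeated for the SOC/PT table, where the default of both periods may apply. On-study KM keeps in the risk set those who stop drug but stay in the study, so it lies closer to the crude value (10.2% against 10.5%, where 10.0% actually stopped).
- Adding the protocol's published death rates to the 9.1% would enlarge the gap but may count deaths twice.
- Dose selection is unlikely to turn on this. The between-arm error is small, the week 16 gap is negligible, and rash in the healthy-volunteer studies appeared 7-10 days after dosing (protocol 2.3.1).

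It is also fair that the hypothetical strategies are openly declared and that protocol 9.4.3 calls all safety analyses descriptive, without p-values.

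**Conclusion.** The point holds in limited form. For any AE leading to discontinuation of IP in the overall summary, the KM% and KM% difference censor events that rule the outcome out, under a strategy that contradicts the endpoint. The direction is certain: KM cannot fall below the actual cumulative incidence and exceeds it once AE stops follow competing events. The size is modest, about 0.4-0.7 points at week 48 (0.28-0.40 SE pooled, 0.20-0.28 SE per arm), and close to zero at week 16 or with early AE stops. These sizes rest on constant hazards, an assumed AE-stop risk of 8-15%, and 9.1% as a stand-in for all competing events.

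The crude n (%), the disposition table and the cause-specific hazard ratio are not inflated. Severity is low. Part B lists the same type of endpoint (protocol 3.2), but its SAP was not available, so nothing is claimed about it.

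**What to change.** In SAP 4.6.2.2, for AEs leading to discontinuation of IP and for the skin-reaction rows defined by IP discontinuation, replace KM% and KM% difference with Aalen-Johansen cumulative incidence and its difference with 95% CI at 16 and 48 weeks. Treat discontinuation for any other reason and death as competing events. Name death explicitly, because SAP 4.1.1.1 counts a participant who dies on drug as having completed treatment. Keep the crude n (%) and the Cox hazard ratio, labelled as cause-specific. In SAP 4.6, state that the strategy under which premature discontinuation cannot occur does not apply to this category.

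The cost is a few lines of SAP text and a standard estimator. Reason for stopping and date of death are already collected, so no further data or participants are needed.
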